7.2.2. Treatment Compliance and Modifications

A subject will be considered compliant if the percentage compliance is between 80% and 120% inclusive, between first and last dose. All treatment compliance will be based on the Safety set.

7.2.2.1. Subcutaneous IP

Overall treatment compliance with SC IP will be assessed by the number of injections actually received versus the number of injections planned. The percentage compliance with SC IP will be calculated as: $100 \times (\text{number taken}/\text{number planned})$. Subjects randomized to SC IP 50 mg q4w take SC IP injections 1 week, and placebo injections 2 weeks later in order to provide blinding from those taking 100 mg q2w. For these subjects, compliance will be calculated irrespective of whether the injection was a placebo or sirukumab dose. The number of planned injections will be calculated based on the subject's last visit.

For example, if a subject's last visit = Week 20, then the planned number of injection will be 11. If this subject only reports 10 injections, the percentage compliance with SC IP will be $100 \times (10/11) = 90.9\%$.

Overall SC IP compliance and compliance categories (0; >0% and <80%; ≥80% and ≤120%; >120%) will be summarized for each treatment group. Compliant subjects (i.e. subjects with a compliance between ≥80% and ≤120%) will be summarized.

In addition, the SC IP / placebo administration will be summarized by treatment groups as following:

- Percentage of subjects who received all SC IP injections
- Percentage of subjects who missed at least 1 SC IP injection

- Percentage of subjects who missed 1/2/3/4/5/6, or more SC IP injections

All SC IP compliance data will be listed.

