3.4. Dose Adjustment/Modifications

No dose adjustment of sirukumab will be allowed in this study.

4. General Statistical Considerations

All analyses detailed in this SAP will be conducted using Statistical Analysis System (SAS)[®] statistical analysis software version 9.3 or higher (SAS Institute, Inc., Cary, North Carolina, USA). All SAS programs used to generate analytical results will be developed and validated according to PPD SAS programming standards and validation procedures.

Summary data will be presented in tabular format by treatment. Continuous variables will be summarized by descriptive statistics including number of subjects (N), mean, standard deviation (SD), median, minimum, and maximum.

Mean and median will be displayed to 1 more decimal place than the measured value. The SD will be displayed to 2 more decimal places than the measured value. Minimum and maximum will be displayed to the same decimal place as the measured value.

Categorical data (such as sex) will be summarized by number and percentage of subjects in each category. Percentages will be suppressed when the count is zero. A row denoted “Missing” will be included in count tabulations where necessary to account for missing values. The denominator for all percentages will be the number of subjects within the treatment (randomized or actual) group for the analysis set of interest, unless otherwise specified. Percentages which differ from 100% will be presented to 1 decimal place and 100% will be presented without a decimal.

Change from Baseline is the post-baseline value minus the baseline value. If the baseline or post-baseline value is missing, then the change from baseline is set to missing. For each scheduled post-baseline time point where change from Baseline is evaluated for continuous variables, descriptive statistics will be displayed for the values at Baseline, values at the scheduled post-baseline time point, and values for change from Baseline at the scheduled post-baseline time point for the set of subjects who have data at both Baseline and the time point being assessed. Early withdrawal visits as well as 16-week follow-up visits are considered as scheduled visits.

In case of multiple assessments for a scheduled visit, the last non missing assessment for this visit will be used for the summaries over time. All results will be listed.

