4.2. Randomization, Stratification and Blinding

Central randomization will be implemented in this study. Subjects will be randomized in a ratio of 3:3:2:2:2 and assigned to 1 of 5 treatment arms in accordance with the computer-generated randomization schedule generated prior to the start of the study, using validated software. Randomization will be performed by an Interactive Response Technology System. Once a randomization number has been assigned to a subject, it will not be re-assigned.

Randomization will be stratified by baseline oral prednisone dose (<30 mg/day or ≥ 30 mg/day). The number of relapsing/refractory subjects will be capped at approximately 50% to ensure that a sufficient number of subjects with new onset disease are recruited.

Blinding will be maintained during the 52-week double-blind treatment phase of this study by the provision of sirukumab and matching placebo for sirukumab in prefilled syringes in a matching presentation. Blinding to the prednisone dose during the taper will be maintained by providing prednisone doses below 20 mg in numbered blister packs. Depending on the subject's assignment to either the 3-, 6-, or 12-month taper, the over-encapsulated dose may or may not contain prednisone. The blister packs contain a combination of over-encapsulated 10 mg, 5 mg, and/or 1 mg prednisone tablets with cellulose filler to prevent rattling and/or placebo capsules containing only the filler. Each subject, regardless of treatment arm, will be provided the same number of capsules per day for a given week to maintain the blind.

Blinding during the q4w dosing regimen will be maintained by the provision of placebo for sirukumab such that subjects randomized to this arm will follow a q2w dosing regimen but alternate between active (starting at Baseline) and placebo treatments for the duration of the 52-week, double-blind phase.

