Exploratory Lab Assessments																			
IL-6 measurements	x	x				x										x			
Blood Biomarkers & exploratory markers		x		x		x			x							x	x	x	
Blood and Urine Markers, Transcriptomics (optional) ¹³	x	x				x			x							x	x	x	
Pharmacogenetics sample ¹⁴		x																	
Exploratory US Imaging																			
Ultrasound imaging ¹⁵	x ¹⁶	x				x										x	x		

1. Including consent for pharmacogenetics.
2. Assuming placebo will also be administered using autoinjector. Additional training may be provided when required.
3. Only for those subjects who initiate open-label sirukumab treatment at the start of Part B.

4. PROs to be completed by subjects before other clinically evaluated assessments or blood draws and before the administration of study drug. At visits where subject is fasting for blood draws, the option exists to perform blood draws prior to completing PROs as necessary to end the fast. HAQ-DI administered only to subset of subjects with PMR. PGA assessed using PtGA (subjects) and PhGA (physicians, after subject completion of questionnaires and after conducting subject assessments).
5. Complete physical exam at Screening and brief physical exam at other time points.
6. Measure in a semi-supine position after 5 minutes rest; includes blood pressure, temperature and heart rate.
7. And when any suspected cardiac abnormality. Average of triplicate recordings.
8. Suggested questions. A QuantiFERON-TB Gold Test should be performed at any time during the study if tuberculosis is suspected.
9. Chest radiograph taken up to 3 months prior to Week 0 may be used to qualify at screening.
10. Pregnancy test: urine = U, serum = S. Premenopausal women only.
11. If hepatitis C antibody positive, a hepatitis C RNA PCR assay should be reflexively performed on a fresh sample to confirm the result.
12. On study drug administration days, PK serum samples must be collected prior to study drug administration. Blood collected from 1 venipuncture will be divided into multiple aliquots of serum for PK serum (sirukumab concentration and antibodies to sirukumab) and backup samples.
13. To be collected only for those subjects consenting to provide samples for the biobank for future exploration of GCA disease biology.
14. Sample should be collected at the Baseline visit but may be collected at any visit post-Baseline if not collected at the Baseline visit.

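### Planned injections are counted through the last visit, with a dose at that visit, so completers, some withdrawals and subjects off drug are tabulated as missing injections that were not due

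*SAP*

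**What the plan says.** SAP 7.2.2.1 defines percentage compliance as injections taken over injections planned. On the denominator it says: "The number of planned injections will be calculated based on the subject's last visit". The worked example takes a last visit at Week 20: "then the planned number of injection will be 11"; with 10 injections reported, compliance is 90.9%. The section does not say which kind of visit counts as the last one.

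The parent section, SAP 7.2.2, gives a different window: "A subject will be considered compliant if the percentage compliance is between 80% and 120% inclusive, between first and last dose".

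SAP 7.2.2.1 then asks for compliance categories, the percentage of subjects who received every injection, the percentage who missed at least one, and a breakdown by number missed.

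The schedule in SAP 13.1, Table 10, marks dispensing of investigational product from Week 0 to Week 48. Week 52 carries a mark only under footnote 3: "Only for those subjects who initiate open-label sirukumab treatment at the start of Part B". The dispensing row is blank under Early Withdrawal and Follow Up. Compliance is assessed from Week 2 to Week 52, at Flare and at Early Withdrawal, but not at Follow Up.

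Arm C has the same injection calendar as the other arms, because "subjects randomized to this arm will follow a q2w dosing regimen but alternate between active (starting at Baseline) and placebo treatments" (SAP 4.2).

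**The concern.** The rule treats the last visit as a dosing occasion. In this trial it often is not. Protocol 5.4.1 asks prematurely withdrawn subjects to attend an Early Withdrawal visit, and SAP 1.1 says that after termination these visits were completed for all subjects. Week 52 of Part A is also Week 0 of Part B (Protocol 7), and subjects in remission stop blinded drug there (Protocol 4.2.2).

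Protocol 5.4.2 also keeps subjects in the study after permanent discontinuation of study drug. For them the last visit can come long after the last dose, and a last-visit denominator counts weeks off drug, including protocol-required stopping, as missed injections.

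At stake is the accuracy of the adherence tables. A subject who took every scheduled dose should be in the row for subjects who missed none. A programmer also cannot satisfy both 7.2.2 and 7.2.2.1 for any subject whose last visit is later than the last dose by one dosing interval or more.

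**Working it through.** **The SAP's own figure.** Injections fall every 2 weeks from Week 0. Counting both Week 0 and the week of the last visit, planned = (week of last visit / 2, rounded down) + 1. For Week 20 this is 20/2 + 1 = 11, and 100 × 10/11 = 90.9%. Both figures reproduce exactly. Week 20 is a dispensing visit, so 11 is correct if Week 20 is the last on-treatment visit.

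**General form.** If a subject took all m injections due and the rule adds k planned injections after the last dose, reported compliance is m/(m + k). This reaches 80% only if m ≥ 4k.

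**Completer.** The last blinded dose is due at Week 50, so the dosing occasions number 50/2 + 1 = 26. The rule gives 52/2 + 1 = 27. Compliance is 26/27 = 96.3%: still compliant, but tabulated as missing one.

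**Early Withdrawal on the next due date (k = 1).**
- Last dose Week 18, withdrawal visit at Week 20: 10/11 = 90.9%, compliant, one missed. This fully adherent subject gives the same result as the SAP's example of a subject who skipped a dose.
- 80% requires m ≥ 4. With 1, 2 or 3 injections the result is 50%, 66.7% or 75.0%; 4/5 = 80.0% passes because the bound is inclusive.
- If the withdrawal visit comes before the next due date, k = 0 and there is no error.

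**A longer gap before Early Withdrawal (assumption).** The documents do not say when injections stopped after termination. If they stopped on 10 October 2017 and the withdrawal visit was as late as 30 November 2017, the gap is 51 days. That covers 3 or 4 due dates, and adherent subjects with fewer than 12 (k = 3) or 16 (k = 4) injections would fall below 80%.

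**Permanent discontinuation with continued attendance.** Ten doses (Weeks 0 to 18), then attendance to Week 52: 27 planned, 10/27 = 37.0%, with 17 shown as missed. Under the 7.2.2 window the same subject has 10/10 = 100%.

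**If the last visit were read as the 16-week follow-up.** With Early Withdrawal 2 weeks after the last dose, k = 1 + 8 = 9: last dose Week 18 gives 10/19 = 52.6%, and last dose Week 50 gives 26/35 = 74.3%. With k = 8 the maximum is 26/34 = 76.5%, and with k = 7 it is 26/33 = 78.8%. Reaching 80% at k = 7 needs 28 injections, and only 26 are scheduled.

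**The case against.** The strongest reply is that the quoted example is not wrong: Week 20 is a dispensing visit, 11 doses are due by then, and the arithmetic is right. That stands. The defect lies in applying the rule to visits where no blinded dose is scheduled, and in leaving the last visit undefined.

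A reader might go further and infer four things that the documents do not support.

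- *That the 16-week follow-up is the last visit, so that no subject can be compliant.* SAP Section 4 does say "Early withdrawal visits as well as 16-week follow-up visits are considered as scheduled visits", but in a paragraph about change-from-baseline summaries. The schedule assesses no product compliance at Follow Up, 7.2.2 ends the window at the last dose, and the example uses a numbered treatment week. The reading is not excluded, but it is unlikely.
- *That nobody can be shown as having received every injection.* This is false where Early Withdrawal precedes the next due date, or where the last visit is an on-treatment dosing visit.
- *That many adherent subjects become non-compliant.* A one-dose excess does this only at three or fewer injections. Larger effects need a longer gap, off-drug follow-up or the follow-up reading, and the documents do not give the distribution of any of these.
- *That safety results depend on it.* Exposure uses first and last injection dates regardless of missed doses (SAP 7.2.1). Treatment-emergent events use the exposed period (9.1). Actual treatment uses the type of injection received (5.1). The analysis sets (4.3), treatment failure (4.6.1) and sustained remission (8.1) do not use the compliance percentage, and none is calculated for Part B (11.2).

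**Conclusion.** The rule in SAP 7.2.2.1 is wrong as written for three groups and contradicts SAP 7.2.2. Adherent completers are reported at 96.3% with one missed injection; this follows directly from the rule and the schedule. Subjects whose Early Withdrawal visit falls on or after the next due date are shown as missing at least one. Subjects who stop drug permanently but remain in follow-up can be shown with very low compliance, 37.0% in the illustration.

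The figures assume two-weekly occasions from Week 0 with the last blinded dose at Week 50, as the schedule implies, and full adherence until drug was stopped. The number of subjects in each group cannot be derived from the documents. The consequence is confined to the descriptive compliance and missed-dose tables for Part A, so this is a minor point.

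**What to change.** In SAP 7.2.2.1, define planned injections as the scheduled two-weekly occasions from the first SC IP injection up to, but not including, the earliest of Week 52, the Early Withdrawal visit or permanent discontinuation of SC IP. A completer then has 26 planned and 26/26 = 100%. A subject last dosed at Week 18 who withdraws at Week 20 has 10/10 = 100%.

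Also:
- state that the 16-week follow-up visit is excluded;
- if the discontinuation date is programmed as the date of the last dose, make clear that this dose still counts as planned;
- reword 7.2.2 so that both sections use the same window;
- label the Week 20 example as an on-treatment dosing visit, for which 11 remains correct.

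The cost is a sentence or two of SAP text and one derivation. No new data are needed.

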7.2.2.2. Prednisone Study Drug

Treatment compliance with prednisone study drug will be assessed by the number of capsules actually taken versus the number of capsules planned, for the blinded taper only. Each dispense will contain enough supply (cards containing the capsules) to cover the period of time until the next scheduled visit plus 1 additional card. The additional card is only to be used if the subject cannot return in time and ensure continuity of treatment (more details in the study procedure manual Section 2.4 Dispensing Study Medication to Subject).

Prednisone study drug – Open-label taper

No compliance will be calculated for the open-label taper.

Prednisone study drug - Blinded taper

The prednisone study drug compliance percentage will be calculated as follows:

$$100 \times (\text{total number of capsules taken} / \text{total number of capsules planned})$$

Total number of capsules taken will be calculated as: Sum of all capsule dispensed from the blinded taper – Sum of all capsules returned from the blinded taper.

The planned number of capsules will be calculated from the blinded tapering schedule:

Blinded Taper Week	Number of planned capsules to be taken per day	Blinded Taper Week	Number of planned capsules to be taken per day	Blinded Taper Week	Number of planned capsules to be taken per day
1	5	16	4	31	4
2	4	17	4	32	4
3	3	18	3	33	4
4	3	19	3	34	3
5	5	20	3	35	3
6	4	21	3	36	3
7	3	22	2	37	3
8	2	23	2	38	2
9	2	24	2	39	2
10	5	25	2	40	2
11	5	26	1	41	2
12	5	27	1	42	1
13	5	28	1	43	1
14	4	29	1	44	1
15	4	30	4	45	1

Overall prednisone study drug compliance and compliance categories (0; >0% and <80%; ≥80% and ≤120%; >120%) will be summarized for each treatment group. Compliant subjects (i.e. subjects with a compliance between ≥80% and ≤120%) will be summarized.

All prednisone study drug compliance data will be listed. Records for the open-label taper will display the number of tablets dispensed and returned and the start and stop dates for dosing. Records for the blinded taper will display the number of tablets dispensed and returned, the start and stop dates for dosing, and the overall percentage compliance calculated for the blinded taper phase.

7.3. Prednisone Intake as a Concomitant Medication

All corticosteroid dosages recorded on the Concomitant Medications - Corticosteroids page in the eCRF will be converted to a prednisone-equivalent average daily dose (mg/day) using a conversion factor for each particular medication. The list will be updated throughout the course of the study to include all corticosteroids taken by the subjects and will be finalized prior to the database lock and unblinding. The conversions of all corticosteroids will be done based on standardized medication name and using the following information from online calculator <http://www.globalrph.com/corticocalc.htm>, retrieved on 24th January 2018

Concomitant Medications with Standardized Medication Name Including the Following Term	Conversion factor for Prednisone - Equivalent Dose (mg)
Cortisone	0,2
Hydrocortisone	0,25
Prednisone	1
Prednisolone	1
Triamcinolone	1,25
Methylprednisolone	1,25
Dexamethasone	6,67
Betamethasone	8,33

Only medications with a unit reported in ‘mg’ will be converted to prednisone.

DOSE2 (prednisone-equivalent dose in mg) = DOSE (collected dose in mg) x conversion factor

DD (daily dose in mg/day) = DOSE2 (prednisone-equivalent dose in mg) x frequency factor

The records from concomitant medication datasets will be mapped to weeks corresponding to the prednisone schedule, e.g. if a subject has prednisone as rescue therapy for 10 days, the first 6 days may be mapped to Week X and the rest of the 4 days will be mapped to Week (X + 1) based on the start and end dates of the rescue medication, as well as the start and end dates of the prednisone tapering schedule at each week.

The following information on corticosteroids taken will be presented in a listing:

- Start and stop dates
- Original units, frequency and dose
- Prednisone-equivalent daily dose (in mg)
- Whether or not it was taken as a rescue medication

- Reason for medication (as collected on the Concomitant Medication-Corticosteroid eCRF page).

Two categories of concomitant prednisone intake will be identified:

- Concomitant prednisone intake as rescue therapy: all concomitant intake of corticosteroids reported for which the question “Was drug administered as a rescue medication?” is “Yes”
- Concomitant prednisone intake for non-GCA-related reasons: all concomitant intake of corticosteroids reported for which the question “Non Giant Cell Arteritis (GCA) related” is ticked

Summary statistics of cumulative prednisone intake including both taper and rescue medication will be summarized by treatment group and visit as well as overall.

Further discussions regarding the statistical analysis of cumulative prednisone intake including both taper and rescue medication is presented in [Section 8.2.1](#).

Frequencies are free text variables and need to be converted to numerical values. The following free text frequencies will be derived as follows:

Text	Frequency used for conversion
1 OF THE 3 DAYS	1/3
2 OF THE 3 DAYS	2/3
BID	2
DAIL	1
DAILY FOR 2 WEEKS	1
DQ	1
EVERY OTHER DAY	1/2
EVERY 12 HOURS	2
EVERY 2 OF 3 DAYS	2/3
EVERY 2 OF THE 3 DAY	2/3
EVERY 2 OF THE 3DAYS	2/3
EVERY 3TH DAY	1/3
EVERY TWO DAYS	1/2
EVERYDAY	1
EVRY DAY	1
MANE	1
ONCE	1
ONCE DAY	1
ONCE A DAY	1
ONCE D AY	1
ONCE EVERY DAY	1
ONCE OVER A DAY	1
ONCE THE DAY	1
ONCE/DAY	1
ONVE A DAY	1
Q3D	1/3
Q8H	3
QD	1
QOD	1/2
TID	3

8. Efficacy Analysis

All efficacy analyses will be based on the ITT set defined in [Section 4.4.3](#), unless otherwise specified. Subjects will be analyzed according to the treatment groups that they were randomized to, regardless of the treatments they actually received.

Only summary statistics will be produced given study termination.

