 - If the year is the same as first SC IP dose in Part A and the end date (after any imputation) is prior to first SC IP dose in Part A, then assume the end date for the start date.

Missing stop/end dates (where UK and UKN indicate unknown or missing day and month, respectively):

- UK-*MMM*-*YYYY*: Assume the last day of the month.
- DD-UKN-*YYYY*/UK-UKN-*YYYY*: Assume 31-DEC-*YYYY*.

In case of the death of the patients and the imputed end date is after the date of death, the stop/end date will be imputed as the date of death.

Completely missing dates will not be imputed.

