8.2. Secondary Efficacy Endpoints

8.2.1. Cumulative Prednisone Dose (Study Drug and Corticosteroid Rescue Therapy) over Time

Cumulative prednisone is the cumulative prednisone dose from the taper (both open-label and blinded) as well as from the corticosteroid rescue therapies, as defined in [Section 3.3](#) and [Section 7.3](#). Cumulative dose at Week X will be derived as the sum of all the doses from baseline to Week X. If a subject withdraw from study between two scheduled visits, all prednisone doses recorded between his last scheduled visit and study withdrawal will be associated to the next scheduled visit. For example, if a subject withdraw between the Week 24 visit and the Week 28 visit, all doses recorded after the day of Week 24 will be associated to Week 28. For more details on imputation of missing data for the key secondary endpoint, please refer to [Section 4.6.3.1](#).

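### SAP 7.3 leaves two steroids with two possible prednisone factors, and its ONCE coding can multiply a single dose whose date is incomplete

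*SAP*

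**What the plan says.** SAP 7.3 converts every recorded concomitant corticosteroid to a prednisone-equivalent daily dose "using a conversion factor for each particular medication". The factor comes from a table whose name column is headed "Concomitant Medications with Standardized Medication Name Including the Following Term". Cortisone has factor 0.2, and the neighbouring rows include "Hydrocortisone 0,25", "Prednisolone 1" and "Methylprednisolone 1,25". No order of precedence is given. Only records in mg are converted.

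The daily dose is the converted dose times a frequency factor. On the latter the SAP says "Frequencies are free text variables and need to be converted to numerical values", and its table gives the bare entry ONCE the value 1, the same as ONCE A DAY and QD. Rescue records are then spread over taper weeks by their start and end dates.

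SAP 4.6.4 completes partial concomitant-medication dates. For a stop date with only the day unknown the rule is "Assume the last day of the month"; with the month unknown it is 31 December. A start date with unknown day becomes the 1st of the month, unless that is the month of the first SC injection. In that month it becomes the first injection date, or the stop date if the record ended earlier.

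The result feeds SAP 8.2.1: "Cumulative dose at Week X will be derived as the sum of all the doses from baseline to Week X". Protocol 9.3.3 names cumulative prednisone dose at Week 52 as the key secondary endpoint.

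**The concern.** There are two separate gaps.

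First, a contained-term match is not unique for nested names. The text of hydrocortisone contains cortisone, and that of methylprednisolone contains prednisolone. A programmer must choose a rule that the SAP does not supply, and the choice changes the factor.

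Second, ONCE coded as 1 per day is harmless if the record covers one day. If the stop date is imputed, one administration is counted on every day up to the imputed stop. SAP 7.2.1 limits SC injection duration to complete dates, and SAP 7.1 says a drug mapped to several ATC terms counts once in cumulative prednisone dose. Neither kind of safeguard is stated for nested names or for single administrations.

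After termination, the by-arm description is the only result for this endpoint. SAP 4 reports mean and SD, and SAP 8.2.1.1 also shows rescue steroid on its own, where an expanded record is not diluted by the taper. One such record could dominate a mean.

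**Working it through.** The plan states no cumulative total or error for this point, so there is no figure to reproduce.

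**1. Name matching.** Comparing the eight listed drug names with the eight listed terms, six match one row and two match two.

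| Drug | Rows matched | Shorter term ÷ own factor | Both rows summed ÷ own factor |
|---|---|---|---|
| Hydrocortisone | 0.2 and 0.25 | 0.2/0.25 = 0.80 | 0.45/0.25 = 1.80 |
| Methylprednisolone | 1 and 1.25 | 1/1.25 = 0.80 | 2.25/1.25 = 1.80 |

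The shorter term is listed first in both pairs. Taking the first match down the table gives −20%. Letting the last match overwrite gives the correct factor. A join that keeps and sums both rows gives +80%.

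**2. Expansion of ONCE.** Contribution = dose × factor × frequency × days, with frequency = 1 and days = stop − start + 1. This assumes that imputed dates are used, which SAP 7.3 implies through its week mapping but does not write out.

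- Complete dates on the same day: 1 day, which is correct.
- Start on day d, stop day missing, month of length L: L − d + 1. The range is 1 to 31, and the mean over all start dates in 2016–2017 is 15.7.
- Both days missing, outside the month of first injection: the 1st to the last day, so 28 to 31 days.
- Both days missing, in the month of first injection: first injection date to month end, so usually fewer days.
- Stop month missing: up to 365, or 366 in a leap year (mean 183.3 over the same start dates), before any cut-off at Week 52 or withdrawal.

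**3. Scale.** The documents give no single rescue dose, so the doses below are assumptions spanning a range. The yardstick is the full 6-month taper from 60 mg. Its open-label weekly doses sum to 260 and its blinded ones to 116, so the total is 7 × (260 + 116) = 2632 mg. The last column divides the excess by the planned 34 subjects of a smaller arm.

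| Assumed single dose | True equivalent (mg) | Counted at 31 days (mg) | Excess (mg) | Shift in mean of 34 (mg) |
|---|---|---|---|---|
| Prednisone 20 mg (×1) | 20 | 620 | 600 | 18 |
| Methylprednisolone 100 mg (×1.25) | 125 | 3,875 | 3,750 | 110 |
| Methylprednisolone 500 mg (×1.25) | 625 | 19,375 | 18,750 | 551 |
| Methylprednisolone 1000 mg (×1.25) | 1,250 | 38,750 | 37,500 | 1,103 |

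As shares of 2632 mg, the shifts are 0.7%, 4.2%, 20.9% and 41.9%. Enrolment stopped early, so actual arms may be smaller and the shift larger. By comparison, the factor ambiguity turns 1250 mg into 1000 mg or 2250 mg for one 1000 mg dose.

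**The case against.** The strongest reply is that the SAP's intention is plain. It speaks of one factor for each medication, both drugs have their own row, and SAP 4 promises validated programs. A reader might infer that the plan prescribes two factors. It does not: it leaves a matching rule unstated, and one natural implementation gives the right answer. This part of the reply stands.

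A reader might also infer that single doses will routinely be inflated 31-fold. That does not follow from SAP 7.3, since complete same-day dates give the correct total. The expansion needs a stop date later than the administration, which in practice means a partial date. No document shows such a record.

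Nor do the documents support a direction of bias between arms. They describe no methylprednisolone pulse regimen. Rescue is investigator-defined (Protocol 4.2.1 and 6.3), the text speaks of rescue prednisone, which matches one row only, and methylprednisolone otherwise appears as an eligibility exclusion (Protocol 5.2). A dose entered in grams would not be converted at all.

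Finally, the frequency table contains misspelt entries such as ONVE A DAY, so it looks built from collected text, and ONCE may be shorthand for once daily. Treating every ONCE record as one dose would cut a genuine 30-day course at 20 mg from 600 mg to 20 mg. This also stands, and it shapes the remedy.

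The reply does not supply a matching rule, or any rule for a single administration with an imputed stop date. The planned corticosteroid listing in SAP 7.3 could expose an error, but no pre-lock review of it is required.

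**Conclusion.** The point holds as a gap in specification. For hydrocortisone and methylprednisolone the factor is correct, 20% low or 80% high, depending on programming that the SAP does not fix. For a true single administration coded ONCE, the rules as written give a multiplier of 1 with complete same-day dates, up to 31 with a missing stop day, and more with a missing stop month.

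The consequence is limited. SAP 1.1 and 8 leave only summary statistics, so no test is at risk. The median and interquartile range are reported and resist a few bad records; the mean and SD do not, least of all in the separate rescue-steroid summary. The conclusion assumes that cumulative dose uses imputed dates. The sizes rest on assumed doses, and whether any affected record exists is unknown. It is worth correcting before lock because the correction is cheap, but it does not cast doubt on the endpoint as a whole.

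**What to change.** Add to SAP 7.3:

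- Each corticosteroid record receives exactly one conversion factor, assigned by full standardised ingredient name or, failing that, by the longest matching term.
- Before database lock and while still blinded, each record with frequency ONCE is checked, by query to the site if needed, and classed as a single administration or as once daily.
- A confirmed single administration counts as one day, whatever its imputed stop date. A once-daily course stays at 1 per day over its recorded dates.

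SAP 7.3 already says that the conversion list will be finalised before lock and unblinding, so the change fits the existing timetable. The cost is a few sentences, a small programming change and a short record check.
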